9.2.1.2 Analysis datasets

The following subsets of study participants will be defined and analyzed:

- 1) The **Safety dataset (SAF)** is defined as those subjects enrolled in the study, who have received at least one dose of study treatment.
- 2) The **Full Analysis Activity dataset (FAS)** is defined as all enrolled subjects who have received all the study treatment (5-low frequency, or 8-high frequency) administrations and have an evaluation of the primary Biological Activity Study End Point.
- 3) The **Per Protocol Activity dataset (PP)** is defined as all enrolled subjects who have been treated consistently with the protocol and have the evaluation of the primary Biological Activity Study End Point available. To be considered evaluable, patients in all study arms must complete at least 2 weeks of study drug treatment.

9.2.2 Statistical Methods

Descriptive statistics for baseline characteristics and study outcomes will be presented in aggregate and stratified by treatment arm, and separately for the SAF, FAS, PP datasets. Descriptive statistics will be implemented as follows:

- 1) Continuous variables will be summarized using the sample mean, standard deviation, and 95% confidence interval for the mean, median, range, and quartiles
- 2) Categorical variables will be summarized using sample proportions and the associated 95% confidence intervals

Simple inferential analysis will be implemented for certain study outcomes:

- 1) Categorical outcomes will be evaluated using simple, ordinal, or multinomial logistic regression.
- 2) Continuous outcomes will be evaluated using linear regression techniques. Quantitative and graphical regression diagnostics will be considered. Data transformations and nonparametric methods will be utilized when necessary.

9.2.4 Analysis of Other Biological Activity Endpoints

Descriptive statistics and simple inferential analyses (as described in 9.2.2) will be provided for all other biological activity endpoints.

9.2.5 Analysis of Safety Endpoints

The safety of r-hCYT107 will be evaluated on all SAF datasets.

9.2.5.1 Adverse Events

Adverse events reported during the study will be coded using the MedDRA terminology.

Treatment emergent adverse events (TEAE) will be defined as any adverse event which occurs or worsens on study treatment during the treatment period.

Numbers and percentages of patients with at least one reported treatment emergent adverse event will be tabulated by system organ class and preferred term for:

- all TEAE
 - all TEAE leading to study drug discontinuation
 - all TEAE of grade 3 or 4
 - all TEAE for which relationship with the study drug is recorded as possible or probable
- by grade
 - all related TEAE leading to drug discontinuation
 - all related TEAE of grade 3 or 4

Recurring adverse events (i.e., adverse events classified with the same preferred term) for a given patient will only be counted once and only their most severe intensity or most severe relationship to the study treatment will be tabulated.

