
Objectives
	
Primary Objective To study the biological activity and safety of two dosing regimens of CYT107 at 10 µg/kg twice a week for the first week, followed by:
 
 • Once a week for the low frequency regimen • Twice a week for the high frequency regimen • Control group: will receive placebo (NaCl 0.9%) twice a week 
Activity The primary objective is to demonstrate that treatment of lymphopenic septic patients with CYT107 will reverse their low absolute lymphocyte count (ALC) which is a marker of immunosuppression and which correlates with mortality. This primary end point, increased, ALC by >50% in septic patients with lymphopenia, will be measured in the control (placebo) and two “dosing frequency” groups at approximately day 42 following randomization and initiation of study drug treatment.
 
Safety To characterize the short term safety in a context of a single cycle of CYT107 (4 weeks) administered according to these two dosing regimens in lymphopenic sepsis patients. Based on the data collected from previous CYT107 studies in Oncology and HIV infection,(12)(13)(14)(15) treatment of lymphopenic sepsis patients with CYT107 is expected to increase the absolute lymphocyte count (ALC) by greater than 50% from baseline by day 42 after therapy is initiated.
 
To date, CYT107 has not been tested in patients with sepsis. Septic patients frequently have decreased kidney and liver function, changes in circulating blood volume, and loss of vascular integrity with leakage of proteins into the interstitial space.(2) These alterations might impact the pharmacokinetics and pharmacodynamics of CYT107. Thus, we will administer CYT107 using a protocol that is highly similar to a previous protocol that was effective in improving the ALC in patients with cancer, HIV, and hepatitis C and was well tolerated with a low incidence of serious adverse effects.(12)(13)(14)(15)(17).
 
The incidence, type and severity of adverse events occurring during the 6 weeks study period will be analyzed for the control arm and two “dosing frequency” groups.
 
Secondary Objectives To characterize CYT107 pharmacokinetics (PK) in patients with sepsis To characterize CYT107 immunogenicity by detection and quantification of binding antibodies and detection of neutralizing antibodies in positive samples To characterize CTY107 pharmacodynamics, specifically to determine if CYT107 can restore depressed functional activity of immune effector cells in patients with sepsis To determine if CYT107 decreases the incidence of secondary infections in septic patients

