Primary Biological Activity & Safety Study Endpoints	
 1) Weekly measures of ALC to determine the kinetic of restoration of adequate absolute lymphocyte count and to validate that CYT107 therapy can increase the ALC by >50% from baseline. The main indicators to be determined are: 
 i) the relative increase in ALC at day 42 expressed as a percentage of baseline value determined at the time point that CYT107 was first administered (day 1) 2) assessment of the clinical, biological and immunological tolerance of CYT107 administration in each group: incidence and scoring of all adverse events (AE) 
 i) biological effects and tolerance (see Appendix Flowchart #3 for all biological/laboratory tests that are to be assessed for CYT107 effects) ii) adverse events (AEs) and serious adverse effects (SAEs) during the duration of the study period will be recorded, ending day 42 +/- 3 																																													

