3.0 Objectives of the Trial

3.1 Primary Objective

To study the **biological activity** and **safety** of two dosing regimens of CYT107 at 10 μ g/kg over a treatment period of 4 consecutive weeks:

Twice a week for the first week, followed by:

- Once a week for the low frequency regimen (plus placebo once a week)
- Twice a week for the high frequency regimen
- Control group: will receive placebo (NaCl 0.9%) twice a week

Activity

The primary objective is to demonstrate that treatment of lymphopenic septic patients with CYT107 will reverse the drop in absolute lymphocyte count (ALC) which is a marker of immunosuppression and which correlates with mortality (see Figure 1 and references 4, 21, 23). The effect of CYT107 on the kinetics of the recovery of ALC will be recorded. CYT107 has been demonstrated to increase ALC in a diverse array of patient populations including patients with HIV, patients who underwent bone marrow transplantation, and patients with cancer. Based on the data collected from previous CYT107 studies in Oncology and HIV infection, the treatment of lymphopenic sepsis patients by CYT107 is expected to produce:

- Primary endpoint: increase of ALC by greater than 50% from baseline by day 42 after CYT107 therapy initiated.
- We will also evaluate the number of patients who restore ALC to >1200 cells/mm³ (the lower limit of normal for ALC at most hospitals) by day 42 with the aim of observing this recovery in more than 50% of the patients

These end points will be measured in the three treatment groups (2 dosing frequencies + 1 placebo) at day 42 in both the French and US studies. All patients will undergo randomization for study drug treatment and undergo all study related tests and procedures.

Safety

To characterize the short term safety in a context of a single cycle of CYT107 (4 weeks) administered according to these two dosing regimens in lymphopenic sepsis patients.

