4.3 Endpoints

4.3.1 Primary Biological Activity & Safety Study Endpoints

- 1) *Weekly measures of absolute lymphocyte counts (ALC)* will be performed to determine the kinetics of restoration of ALC. Specifically, we will quantitate the increase of ALC at day 42 +/- 3 days, expressed as a percentage of baseline value determined at the time point that CYT107 was first administered (day 1). We will determine the number of patients who reach a 50% increase over the baseline value and we will also determine the percentage of patients reaching an ALC > 1200 at day 42 +/- 3 days in each group.
- 2) *Assessment of the clinical, biological, and immunological effects of CYT107* as well as its safety and tolerability, i.e., incidence and scoring of all adverse events: AEs and SAEs all over the study period, ending day 42 +/- 3 days, will be recorded and evaluated by the DSMB, Steering Committee, and secondary infections committee.

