4.4 Duration of the study

Patients will be treated with CYT107 or placebo for 4 weeks duration and undergo laboratory monitoring of various organ functions as detailed previously for the 28 days following the initial treatment. The ALC will be followed for an additional 14 days due to continuing effects of CYT107. Primary end points will be measured at approximately Day 42 +/- 3 days. Patient outcomes regarding secondary infections, readmission to hospitals, mortality, etc. will be followed at approximately 60, 90, 180 and 365 days after CYT107 therapy is initiated. Long term survival (1 year survival) will be recorded using a variety of means including physician records, patient telephone communication, and searches of mortality databases.

5. Study Population

5.1 Inclusion Criteria:

- 1) Patients of age ≥ 18 yrs to 80 yrs
- 2) Patients with persistent suspected sepsis at 48-120 hrs after admission
- 3) Two or more criteria for the systemic inflammatory response syndrome (SIRS) (see reference (19) for SIRS criteria) and a clinically or microbiologically suspected infection.
- 4) At least one organ failure as defined by a SOFA score of ≥ 2 at any time point during the 48-120 hrs after admission to the ICU
- 5) Requirement of vasopressor treatment as follows: i) epinephrine or norepinephrine at ≥ 0.05 $\mu\text{g}/\text{kg}/\text{min}$ ideal body weight; ii) vasopressin, or iii) dopamine at $\geq 4-5$ $\mu\text{g}/\text{kg}/\text{min}$ ideal body weight, continuously for 4 hrs or more, provided that at least 20 ml/kg of ideal body weight of crystalloid or an equivalent volume of colloid was administered during the 24-hour interval surrounding the start of vasopressor treatment, to maintain systolic pressure ≥ 90 mmHg or a mean arterial pressure ≥ 60 mmHg at any time point during their sepsis course preceding enrollment into the CYT107 study.
- 6) Lymphopenia with an absolute lymphocyte count ≤ 900 cells/ mm^3 at either the day of consent or the day prior to consent during their ICU stay
- 7) Predicted length of stay in the ICU of up to two weeks after starting drug therapy treatment in the trial
- 8) Ability to obtain a signed informed consent from patient or LAR consent.

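### On the protocol's 4-week treatment period, the planned adverse event tables leave out the last two of the six weeks promised for analysis, and none identifies serious events

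*Protocol*

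**What the plan says.** Protocol 9.2.5.1 is the only place that specifies AE tables. It defines a treatment-emergent AE (TEAE) as "any adverse event which occurs or worsens on study treatment during the treatment period" and lists six tables, all restricted to TEAEs: all events; events leading to drug discontinuation; grade 3 or 4 events; possibly or probably related events by grade; related events leading to discontinuation; and related grade 3 or 4 events. The section gives no end date for the treatment period.

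Other sections supply a length. Section 3.1 describes the regimens "over a treatment period of 4 consecutive weeks", and section 4.4 says "Patients will be treated with CYT107 or placebo for 4 weeks duration". Figure 8 in section 4.2 shows a treatment phase followed by a separate follow-up phase.

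The safety commitments are wider. Under Objectives, the synopsis says that the incidence, type and severity of "adverse events occurring during the 6 weeks study period will be analyzed for the control arm" and for the two dosing-frequency groups. The synopsis endpoint list says "adverse events (AEs) and serious adverse effects (SAEs) during the duration of the study period will be recorded, ending day 42 +/- 3". Section 4.3.1 says "AEs and SAEs all over the study period, ending day 42 +/- 3 days, will be recorded and evaluated by the DSMB".

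Section 9.2.2 makes a general promise: "Descriptive statistics for baseline characteristics and study outcomes will be presented in aggregate and stratified by treatment arm", with the safety dataset among those covered. It names no AE or SAE table. The SAP names mortality as an outcome but lists no AE or SAE analysis.

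**The concern.** Safety is part of the primary objective, and section 2.4.3.2 says the drug has not been tested before in sepsis. If the TEAE rule is run as written with a 4-week treatment period, the tables show four weeks of events where the synopsis promises six.

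The protocol itself expects drug activity in the omitted weeks: "The ALC will be followed for an additional 14 days due to continuing effects of CYT107". Those weeks contain the day 29 and day 42 assessments in section 6.3.2. They also contain the only spleen ultrasound after dosing in section 7.1, at about day 42. Section 12.1 allows an abnormal imaging result to be an AE. One with onset dated at that scan would enter none of the incidence, severity or relatedness tables.

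Separately, SAEs belong to the primary safety endpoint, and section 12.2.1.2 requires seriousness to be recorded for each event. Even so, no listed table shows how many patients in each arm had a serious event. Grade 3 or 4 is not a substitute, because section 12.1 defines serious by outcome, including prolonged hospitalization and medical significance.

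**Working it through.** The plan states no figure to reproduce here. The check compares the text and counts days.

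**Inputs**
- End of treatment period: day 28 (4 weeks, sections 3.1 and 4.4). This is an inference, because 9.2.5.1 gives no end.
- End of safety window: day 42, with the visit between day 39 and day 45 (synopsis endpoints and section 4.3.1).
- Last scheduled dose: day 25 (section 8.5).
- Scheduled assessments: days 4, 8, 15, 22, 29 and 42 (section 6.3.2).
- Listed AE tables: six (section 9.2.5.1).

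**Time outside the tables**, as (end of safety window − end of treatment) / end of safety window:
- Visit on day 42: (42 − 28)/42 = 14/42 = 33%.
- Visit on day 39: (39 − 28)/39 = 11/39 = 28%.
- Visit on day 45: (45 − 28)/45 = 17/45 = 38%.

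If the window closed at the last scheduled dose instead:
- Visit on day 42: (42 − 25)/42 = 17/42 = 40%.
- Visit on day 39: (39 − 25)/39 = 14/39 = 36%.
- Visit on day 45: (45 − 25)/45 = 20/45 = 44%.

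**Tables affected.** An event that leads to drug discontinuation has to arise while dosing is under way, so the two discontinuation tables are essentially unaffected. That leaves 6 − 2 = 4: all TEAEs, grade 3 or 4, related by grade, and related grade 3 or 4.

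**Assessments affected.** Days 29 and 42 fall after day 28: 2 of 6.

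**Seriousness.** The six tables select on occurrence, discontinuation, grade and relationship. Tables selecting on seriousness: 0 of 6. Serious events during treatment are counted among all TEAEs but cannot be told apart there.

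**Whether another section closes the gap.** The opening sentence of 9.2.5.1 covers all events reported during the study, but only for MedDRA coding. Sections 9.2.5.2 to 9.2.5.4 summarize laboratory tests, vital signs, physical and lymphoid examination and ECG; they do not name AEs or the spleen ultrasound. Section 9.2.2 gives no AE window. The SAP's Fisher exact test for mortality covers deaths, not other serious events.

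**The case against.** The strongest reply is that the six-week analysis is already promised. The synopsis says so, section 4.3.1 makes AEs and SAEs to day 42 +/- 3 an endpoint, section 9.2.2 commits to describing outcomes by arm, and nothing says that the list in 9.2.5.1 is exhaustive. On that view, a table is unnamed and no events are excluded by decision. It is also true that the treatment period has no stated end, so the day-28 cutoff is an inference.

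Both points are fair as far as they go. But 9.2.5.1 is the only AE table specification, and a programmer following its definition would drop the later events. The undefined end does not rescue the plan: closing the window at the last dose widens the gap, as would closing it at hospital discharge, when dosing stops.

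Three further points hold in part. Events first noted at the day 29 visit may have started earlier and would still count. The spleen example requires the finding to be declared an AE with onset dated at the scan, and under section 10.2 the DSMB sees individual data on lymphoid organ size. SAEs are reported within 24 hours and reviewed by the DSMB. These points limit the consequences for patient oversight. They do not supply a tabulation by arm. The SAE table and the sensitivity version are useful additions, and the case for change does not rest on them.

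**Conclusion.** The point holds. The TEAE definition in 9.2.5.1 is narrower than the synopsis commitment, and neither the rest of the protocol nor the SAP reconciles the two. With the treatment period taken to end on day 28, 14 of 42 days (33%; 28% to 38% across the visit window) fall outside four of the six AE tables, and none of the six identifies serious events. How many events this concerns cannot be derived from the documents.

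AE recording, DSMB and Steering Committee review, the laboratory, vital-sign, lymphoid-examination and ECG summaries, and the mortality analysis are not affected. The change should be made before the analysis, but the data are not at risk.

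**What to change.** In Protocol 9.2.5.1, define the AE tabulation window as events that start or worsen from first dose through the day 42 +/- 3 visit, whatever the patient's dosing or discharge status. Apply it to the AE tables by arm on the safety dataset; in practice it changes the four incidence, severity and relatedness tables. Add one SAE table by arm for the same window. Keep the on-treatment versions of those four tables as a sensitivity analysis, with the end of the treatment period stated.

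The cost is one definition, one extra table and a second version of four tables. No new data are needed: section 12.2.1 already has AEs recorded from consent to the End of Study Visit, and seriousness is captured for each event. The downside is that more background sepsis events are counted in all three arms. The on-treatment versions let a reader see how much that matters.

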9.2.5.2 Safety laboratory tests

Descriptive statistics for laboratory safety tests will be computed at each time points on the raw values. If relevant for some parameters, changes from baseline will also be tabulated.

Shift tables from baseline will be presented.

9.2.5.3 Vital signs

Descriptive statistics will be computed at each time point on the raw values.

9.2.5.4 Other safety variables

For Physical and lymphoid examination and ECG; descriptive statistics will be provided at each time point.

9.2.6 Concomitant Treatments

Concomitant treatments will be coded with the WHO-DRUG dictionary and the ATC classification. They will be tabulated by the anatomic, therapeutic and clinical level.

9.3 Statistical Analysis Plan

A Statistical Analysis Plan (SAP) will be written, validated and signed before the first interim analysis. This document will describe the detailed methodology for statistical analyses of the data collected in both US and French studies.

An interim analysis will be performed when the last patient of both IRIS-7A and IRIS-7B studies (i.e. the 30th patients of the two cumulated studies) will reach day 60, then the database will be locked and the study unblinded for analysis.

Final analysis including follow up controls will be performed when the last patient of both IRIS-7A and IRIS-7B studies (i.e. the 30th patients of the two cumulated studies) will reach day 360, then the database will be definitively locked for final data analysis.

10. Trial Organization

10.1 Steering Committee

A steering committee will be set up with the following members:

- Study Chairman
- Investigator from each center
- Medical representative from Revimmune
- Other external participants, as needed

This committee will meet under various circumstances:

On an ongoing basis, the Steering Committee will review all Grade ≥ 3 Adverse Events, and Critical Event.

Upon request of the Sponsor and of the DSMB recommendation to evaluate:

- Potential amendment
- Statistical analysis plan
- Results of interim analyses
- Study continuation

At the end of the study to review the activity and safety data

The steering committee meetings can be organized as a conference call.

10.2 Data Safety Monitoring Board (DSMB)

The DSMB will be composed of 4 experts who are not involved in the conduct of this trial as investigators but are experienced in the management of Sepsis disease and immunotherapy:

- [name], MD, Brown University School of Medicine, USA
- [name], MD, Vanderbilt University School of Medicine, USA
- [name], PhD, Vanderbilt University School of Medicine, USA
- [name], MD, University of Florida School of Medicine, USA

If need be, the DSMB is free to ask for the advice of one or several other experienced physicians whose name and advice, however, must be communicated to the steering committee.

The mission and rules of DSMB is described in the DSMB charter which will be signed by DSMB member before study initiation.

On an ongoing basis, the DSMB will review:

- All Critical Events.
- All treatment emergent adverse events (TEAEs)
- All SAE assessed by the investigator, by the DSMB, UVEC or by the 3 panel expert committee which adjudicates whether the abnormal finding is secondary to CYT107 or part of the septic process.
- Individual data on the size of lymphoid organs.

The DSMB will review, confirm or discuss the severity grade suggested by the investigator assess the causality relationship to CYT107 and the experimental protocol.

The DSMB will advise the Sponsor regarding study continuation. On an ongoing basis and at the end of the study the DSMB, will review the safety data.

The experts of the DSMB should follow and complete the Causality Assessment Guidelines.

10.3 Secondary Infections Evaluation Committee

Because it is often difficult to determine if a secondary hospital acquired infection is present, a panel of 3 experienced ICU physicians will be used to evaluate and grade whether a secondary hospital acquired infection is present. These members include: [name], Professor of Surgery, Washington University School of Medicine; [name], Assistant Professor of Anesthesiology and Critical Care Medicine; Washington University School of Medicine. [name], Assistant Professor of Anesthesiology and Emergency Medicine. Washington University School of Medicine.

These 3 physicians will be blinded to patient treatment with CYT107 versus placebo. They will not be members of the investigative team but rather colleagues of the investigators. They will meet either in person or by teleconference once a month to judge secondary infections.

11. Procedures for Special Events

